4.0 OVERVIEW OF STUDY DESIGN/INTERVENTION

4.1 Design

Accrual: In 2011, a total of 825 patients were treated at MSKCC for a brain tumor with surgery, radiation therapy (n=286+) and/or chemotherapy (Caisis database, accessed 3/1/2012). In 2010 and 2011, a total of 86 patients had suspected radiation injury and underwent surgical resection of their lesions (outcomes consisted of "recurrent/residual tumor with treatment effect" and "non-cancer" diagnoses at histopathology). The ratio of nonsurgical vs. surgical treatment for patients with suspected radiation necrosis at MSKCC is estimated at 2-3:1, based on our recent study³⁶ on suspected pseudoprogression (early radiation injury in high grade glioma patients) and observed patterns from imaging studies and multidisciplinary tumor board discussions. Extrapolating from the 86 patients with suspected radiation injury and subsequent histopathology, we estimate that approximately 258-344 patients over 2 years undergoing brain tumor treatment at MSKCC may have a concern of radiation injury. Based on accrual rates for similar protocols at MSKCC, and our accrual rate thus far (75 patients over 2 years), the estimated accrual for this study is 2-4 patients per month. We plan to enroll approximately 35 patients per year, for a total of 150 patients over a 4 year period. We will continue to follow up until death or a year after the patient's last MRI if he/she is lost to follow up.

The study will prospectively enroll patients who have increasing size and/or enhancement of brain lesion(s) after brain radiation therapy for a neoplasm (either primary or metastatic), where it is unclear if a lesion represents radiation injury or progressive tumor. The procedures and the minimal risks of MRI perfusion and PET/CT are the same regardless of the situation (tumor type or radiation plan) in which they are applied. We apply identical processing procedures to analyze the data regardless of the original tumor type or radiation therapy regimen, and when applicable apply identical imaging metric thresholds. Radiation injury may occur after stereotactic radiosurgery, partial brain

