11.1 Entire cohort analyses

Despite the heterogeneity of potential tumor types, radiation injury has a common mechanism in all patients: blood brain barrier disruption, inflammation, gadolinium contrast leakage into the interstitial space, and enhancement. In most clinical scenarios, we expect lower MRI perfusion and lower FDG PET/CT measurements for radiation injury regardless of the original tumor type. When considering the target accrual of 150 patients with indeterminate lesions, we anticipate that tumor progression will occur more commonly (approximately 90 patients) than radiation injury (approximately 42 patients) or uncertain diagnoses (approximately 8 patients). We anticipate that only 20-30% (28-42 patients) will require the entire 6 month follow up period to establish their diagnosis. Some patients may require >6 months and be followed up to 1 year to establish their diagnosis. Loss to follow up or death prior to determining a definitive diagnosis is expected to be uncommon (<5 patients). Unless an autopsy is performed to render a diagnosis for the brain lesion, death will be a criterion for removal from the study as described in Section 10.

We will perform one-sided two-sample t-tests (because previous analysis showed that MRI perfusion measurements are reasonably symmetric, have a small range and are usually lower in radiation injury than in tumor progression). To approximately assess the power of the analysis, we focus on the one-sided two sample t-test with the type I error

(claiming a difference while there is not) rate of 5%. With 150 patients over 2 years and assuming the effect size is 0.5 (meaning that the difference is half of the pooled standard deviation), type II error (failure to detect a difference that actually exists) rate is about 10%. If the effect size is 0.7, the type II error rate is about 1%. Here we used generic mean/standard deviation ratios because multiple measurements will be examined.

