An interim analysis is also planned at half of the expected total. An O'Brien-Fleming boundary will be used to ensure the type I error rate is not inflated. Specifically, this requires the p-value must be <0.0088 at the interim analysis to stop the trial early and declare statistical significance and <0.0467 at the final analysis to declare statistical significance. Moreover, if the interim analysis p-value is >0.50 then we will stop the trial and declare futility. Under null hypothesis (that tumor and necrosis cannot be differentiated by the new imaging method) the early stopping probability is 0.5 for declaring futility and is 0.0088 for declaring significance. Under the alternative hypothesis with the effect size of 0.7, the early stopping probability is 0.002 for declaring futility and is 0.69 for declaring significance.

To quantify predictive power of the MRI perfusion package, receiver operating characteristic (ROC) analyses will be used.

For the analysis of PET/CT, similar approaches will be used. To compare the predictive power of various MRI perfusion measurements and PET/CT measurements, ROC curves will be drawn, and the area under the curve (AUC) will be computed and compared among MRI perfusion and PET/CT measurements. Bootstrap confidence intervals will be constructed to establish confidence levels and the difference between the two AUCs will be calculated and examined whether it is significantly different from 0. Due to the multiple comparisons needed, a false discovery rate (FDR) approach will be employed to control for the family-wise error rate. The positive FDR approach will yield new quantities called q-values for making statistical inferences.^{53, 54} The purpose of implementing an FDR approach is to adjust the p-values from multiple tests (due to multiple MRI perfusion and PET/CT parameters to be examined).

For the exploratory objective to examine increasing non-enhancing masses, similar analyses will be done. We estimate 5-10 patients with recurrent tumors may receive antiangiogenic therapy. If the numbers are small, we will summarize the results descriptively and suggest future research directions. If the numbers are sufficient, we will perform similar sensitivity, specificity, ROC and AUC analyses.

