To further consider the variation among radiation doses, fractionations and schedules (which may be employed as per the standard of care for the specific tumor type in each patient), a more complicated ANCOVA (analysis of variance with covariates) will be used with the above parameters specified as covariates. If the numbers are small, we will summarize the results descriptively and suggest future research directions. We estimate that 15-25% (21-35 patients of the total) will undergo repeat surgical resection or biopsy to determine the diagnosis. A separate subset analysis will examine for potential differences between lesions diagnosed by pathology vs. lesions diagnosed by clinical and radiological follow up.

Most of the time, the two imaging methods (i.e., MRI perfusion and PET/CT) are expected to yield concordant results (>80%). Therefore, it is meaningful to compare the predictive power of various MRI perfusion measurements and PET/CT measurements. Due to the multiple comparisons needed, an FDR approach will be employed to control for the family-wise error rate. We may further construct a decision rule by combining results from both techniques in the hope of identifying an even more powerful predictive tool, although its feasibility would depend on the exact number of discordant cases and the individual

predictive power (if both MRI perfusion and PET/CT have sufficient predictive power and there are too few discordant cases then the combination may not show significant improvement).

As mentioned above, an interim analysis will be performed after 1 year or accrual of 48 (1/2 of expected total) subjects. Statistical tools may be adjusted at that time point if necessary to account for higher or lower than expected accruals within subgroups. For example, if many more than expected patients have uncertain outcomes or death before diagnosis (without autopsy), then we will may increase the target accrual to compensate.

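### The interim look is set at 48 patients or 1 year and labelled half of the total, but half of the 150-patient target is 75

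*Combined protocol and SAP*

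**What the plan says.** Section 4.1 gives the size and pace of the study: "We plan to enroll approximately 35 patients per year, for a total of 150 patients over a 4 year period", and "the estimated accrual for this study is 2-4 patients per month". It also reports that 75 patients had been accrued over 2 years when this text was written. Section 11.1 repeats the size ("When considering the target accrual of 150 patients with indeterminate lesions"), but its power statement uses a different duration: "With 150 patients over 2 years and assuming the effect size is 0.5".

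Section 11.1 then sets up one interim look: "An interim analysis is also planned at half of the expected total". Success requires p below 0.0088 at the look and below 0.0467 at the end. For futility, "if the interim analysis p-value is >0.50 then we will stop the trial and declare futility". At effect size 0.7, "the early stopping probability is 0.002 for declaring futility and is 0.69 for declaring significance".

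Later the same section refers back to this look and gives it a number: "an interim analysis will be performed after 1 year or accrual of 48 (1/2 of expected total) subjects". It allows target accrual to be raised at that point.

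**The concern.** The count of 48 and its label sit in one parenthesis and cannot both be right against a target of 150. The trigger decides when a success rule and a futility rule are applied. Someone following the boundary paragraph would look at 75, and someone following the later paragraph would look at 48 or after a year. The second reader would use cut-offs derived for a different information fraction, with operating characteristics that differ from those stated. The main risk is an early futility stop for a measurement that does separate the two diagnoses.

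**Working it through.** **1. The label.** 150 / 2 = 75. 48 / 150 = 0.32. 2 × 48 = 96, and no section gives 96 as a total.

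**2. The 1-year alternative.** Section 4.1's monthly rate gives 12 × 2 = 24 to 12 × 4 = 48, and its annual figure gives about 35. Only Section 11.1's 150 over 2 years would give 75, and Section 4.1 says 4 years.

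**3. Cut-offs.** For a two-look O'Brien-Fleming design with one-sided 5% error (Section 11.1), solve P(Z1 > c/√t or Z2 > c) = 0.05, where Z1 and Z2 are standard normal with correlation √t.
- t = 0.50: c = 1.678, so p = 0.0088 and 0.0467. The plan's figures are reproduced.
- t = 0.32: c = 1.652, so p = 0.0017 and 0.0493.

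**4. Stopping probabilities at the look.** Let θ = d√(n1·n2/(n1+n2)). Success is Φ(θ − 2.374), where 2.374 is the normal quantile for 0.0088. Futility is Φ(−θ), since one-sided p > 0.50 means Z < 0. The split is taken as 2:1, or as Section 11.1's expected 90 progression to 42 injury, with 1:1 as the most favourable case. Every counted patient is assumed to have a diagnosis.

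| Patients at look | Split | Success, d = 0.7 | Futility, d = 0.7 |
|---|---|---|---|
| Plan's statement | not given | 0.69 | 0.002 |
| 75 | 2:1 | 0.686 | 0.0021 |
| 75 | 90:42 | 0.674 | 0.0024 |
| 48 | 1:1 | 0.520 | 0.0077 |
| 48 | 2:1 | 0.465 | 0.0111 |
| 48 | 90:42 | 0.454 | 0.012 |
| 35 (1 year) | 2:1 | 0.337 | 0.0255 |

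The exact noncentral t gives success of 0.666 and 0.654 for the two rows at 75, and 0.427 (90:42) to 0.491 (1:1) at 48.

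**5. Which numbers fit 0.69?** Φ(θ − 2.374) = 0.69 needs θ = 2.870. With f the fraction in the smaller group, N = (2.870/0.7)² / [f(1 − f)] = 16.81 / [f(1 − f)]. This is 67 at 1:1, 76 at 2:1 and 77 at 90:42. By exact t, 70 patients at 1:1 give 0.689 and 0.0017.

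**6. What a look at 48 does with the stated cut-offs.**
- Type I error at t = 0.32 is 0.0479 with binding futility and 0.0517 without. At t = 0.50 the figures are 0.0489 and 0.0500.
- False futility at d = 0.5, 2:1 split: at 75, θ = 0.5√(50·25/75) = 2.041, giving 0.0206. At 48, θ = 0.5√(32·16/48) = 1.633, giving 0.0512. At 35 it is 0.0816.
- Type II error at d = 0.5, final split 100:50: with binding futility, 0.116 for a look at 75 and 0.138 for a look at 48. With non-binding futility it is 0.111 for both.

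**7. Enrolled or diagnosed?** Section 11.1's expected outcomes are 90 + 42 + 8 = 140, of which 132 are usable. Of 75 enrolled, 75 × 132/140 = 71 would be diagnosed, or 75 × 132/150 = 66 if only 132 of the 150 are. At d = 0.7 and 90:42, success is 0.64 and 0.61 respectively (0.62 and 0.59 by exact t), and futility is 0.003 and 0.004.

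**The case against.** The case for leaving this alone is that little is lost. Type I error stays within about 0.2 percentage points of 5%. Type II error moves only if futility is binding, and then by about 2 points. With 75 patients already accrued, rewording the trigger may change nothing in practice. All of this stands and limits the weight of the point. It does not make 48 half of 150, and the plan's wording on futility reads as binding.

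Three stronger readings are tempting, and the documents do not support them.
- A reader might infer that the stated stopping probabilities single out 75. They do not. The fit depends on split and formula, and 70, which is half of the 140 that Section 11.1's outcome counts add up to, fits at 1:1 by exact t. The probabilities rule out 48. The case for 75 rests on the stated target and the stated half.
- A reader might infer that putting 75 in place of 48 leaves every stated figure intact. That holds, approximately, only if the 75 all have a diagnosis. Section 7.3 requires at least 6 months of follow-up before a lesion not sampled can be called radiation injury, so recent enrolments would not yet count and the figures in step 7 could be lower still.
- A reader might infer that error control is lost. Step 6 shows that it is not.

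**Conclusion.** The trigger is wrong as written and should be fixed. Both paragraphs intend a look at half, the target is 150, and neither 48 nor, at Section 4.1's rate, 1 year meets that description. The cut-offs belong to 50% information.

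The effect is moderate. At d = 0.7 the chance of an early success stop falls from the stated 0.69 to 0.43-0.52. At d = 0.5 and a 2:1 split, false futility rises by a factor of 0.0512/0.0206 = 2.5. The consequence figures assume a normal approximation, a 2:1 split, and a diagnosis for every patient counted; the range at 48 covers 1:1 to 90:42 and both formulas.

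The documents do not say whether a look has been taken. Both triggers in Section 11.1 have passed on Section 4.1's figures, yet the look is still described as future.

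**What to change.** In Section 11.1, replace the 48-or-1-year trigger with one number, 75 (half of 150), delete the 1-year alternative, and state that the count is of patients with a tumor or radiation-injury diagnosis. If enrolled patients are to be counted instead, restate the d = 0.7 stopping probabilities for the number expected to be diagnosed (about 66-71 of 75: success 0.59-0.64, futility 0.003-0.004).

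Add a sentence saying whether a look has been taken and at what number. If the look was not at half of the final total, counted in the same unit and after any increase in target accrual, re-solve the final cut-off at the actual information fraction under the futility rule as applied. This matters even with the corrected trigger: if 150 enrolled yield 132 to 150 × 132/140 = 141 diagnosed, then 75 diagnosed is 53-57% of the final information.

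The cost is one phrase and one or two sentences. The downside is a somewhat later look: 75 − 48 = 27 more patients, plus the wait for their diagnoses. With 75 already accrued, the delay should be small.

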Specifically, to be classified as radiation injury, the lesion must spontaneously stabilize (stable disease) or decrease (partial response or complete response) on subsequent scans over a minimum of 6 months without new chemotherapy. Lesions that continue to increase (fulfilling criteria for progressive disease) will be considered tumor. If the lesion is stable for <6 months and therefore does not meet above criteria for radiation injury, it will be placed in a third category of uncertain and may be excluded from statistical analysis, unless additional follow up beyond the 6 months shows stability (radiation injury) or enlargement (worsening tumor). Therefore, the designation of uncertain may be only temporary, as we will continue to follow the lesion and the patient whenever possible. If a lesion has an uncertain diagnosis despite continued follow up at the end of the study, it will also be placed in the uncertain category and may be excluded from statistical analysis.

Patients with metastatic disease who have enhancing lesions and receive chemotherapy for systemic disease may be determined to have radiation necrosis if: 1) the systemic chemotherapy does not change during the 6 month follow up period to establish radiation necrosis; and 2) the systemic chemotherapy has no known efficacy for CNS disease. If the lesion diagnosis is uncertain after follow up for reason, including interval changes in systemic chemotherapy or additional radiation therapy for new lesions (unrelated to the initially treated lesion that is being followed) as per their treating physician and the

^{*}Progression occurs when this criterion is present.

florease in corticosteroids alone will not be taken into account in determining progression in the absence of persistent clinical deterioration.

standard of care, then the treated lesion will be placed in the third category of uncertain and excluded from statistical analysis.

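### The interim look is triggered by accrual or elapsed time although a follow-up injury label takes at least 6 months, so the stopping probabilities stated for effect size 0.7 do not hold

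*Combined protocol and SAP*

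**What the plan says.** Section 11.1 sets the test: "We will perform one-sided two-sample t-tests", at an overall type I error of 5%. One interim look uses an O'Brien-Fleming boundary. The trial stops for success at p < 0.0088 and for futility at p > 0.50. For effect size 0.7 the section states that "the early stopping probability is 0.002 for declaring futility and is 0.69 for declaring significance". Under the null it gives 0.5 and 0.0088.

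The timing appears twice in Section 11.1: first as half of the expected total, then as "an interim analysis will be performed after 1 year or accrual of 48 (1/2 of expected total) subjects". Neither statement ties the count to diagnosed patients.

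Section 7.3 defines the follow-up labels. Injury requires stability or shrinkage "on subsequent scans over a minimum of 6 months without new chemotherapy". A lesion stable for less time is uncertain and may be left out of the analysis. A lesion that keeps growing and meets the progression criteria is called tumor, and that section states no minimum time for it. Pathology can settle either diagnosis sooner; Section 11.1 expects it in 15-25% of patients.

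On pace, Section 4.1 says "the estimated accrual for this study is 2-4 patients per month". It also reports 75 patients over 2 years so far (75/24 = 3.1 per month) and plans about 35 per year.

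**The concern.** The interim test compares lesions labelled tumor with lesions labelled injury, but its timing counts people enrolled. Injury is the rarer outcome (Section 11.1 expects about 42 cases against 90 tumors), and it is also the one that must wait. Patients enrolled in the 6 months before the look can contribute tumor labels but, without pathology, no injury labels. The look therefore has fewer injury lesions than its nominal size implies.

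Two things are at stake. The plan tells its readers that a useful imaging measure has a 0.69 chance of early success and a 0.002 chance of being dropped for futility. If those figures are wrong, the case for having the look is wrong too. And the futility rule ends the trial, so a higher chance of a wrong futility stop is a real loss.

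**Working it through.** **1. Reproduce the plan's figures.** With nT tumor and nI injury lesions and effect size d, the noncentrality is d·√(nT·nI/(nT+nI)). P(success) is the chance that the one-sided t-test gives p < 0.0088; P(futility) is the chance that p > 0.50.

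- Final analysis: "With 150 patients over 2 years and assuming the effect size is 0.5" the plan gives a type II error of about 10%, and "If the effect size is 0.7, the type II error rate is about 1" per cent. A 100/50 split gives 0.107 and 0.008 (normal approximation), so both reproduce.
- Interim: 75 patients split 50/25 give 0.7·√(1250/75) = 2.86. P(success) is 0.69 (normal) or 0.67 (t), and P(futility) is 0.002.

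The plan does not state the split; 2:1 is inferred from the fit. A 35/35 split also fits (0.689 and 0.0017 by t). Either way, the stated pair describes 70 to 75 patients who all have labels.

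**2. Share enrolled in the last 6 months** (uniform accrual, clock from enrolment): 6 × rate / N.

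- 48 accrued: 12/48 = 25% at 2 per month; 18.6/48 = 39% at 3.1; 24/48 = 50% at 4.
- 1-year trigger: 6/12 = 50% at any uniform rate.
- 75 accrued at 3.1 per month: 18.6/75 = 25%.

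Reaching 48 takes 24, 15.5 or 12 months at 2, 3.1 or 4 per month. If the earlier trigger governs, the 1-year one is never the later.

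**3. Expected labelled counts.** Section 11.1's expected outcomes (90 tumor, 42 injury, 8 uncertain) sum to 140, giving shares of 64.3% and 30%. Let R = 6 × rate. Assumptions: 0-20% of recent injury cases are labelled early, 50-100% of recent tumors are labelled, and there is one lesion per patient.

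- nI = 0.30 × [(N − R) + (0 to 0.2)·R]
- nT = 0.643 × [(N − R) + (0.5 to 1)·R]

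For N = 48 at 3.1 per month, R = 18.6. Then nI = 0.30 × 29.4 = 8.8, up to 0.30 × 33.1 = 9.9; nT = 0.643 × 38.7 = 24.9, up to 0.643 × 48 = 30.9. The noncentrality is 1.79 to 1.92.

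**4. Stopping probabilities at effect size 0.7** (noncentral t):

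| Look | Injury labels | P(success), with lag | P(futility), with lag | P(success) / P(futility), all labelled |
|---|---|---|---|---|
| 48 accrued, 2 per month | 10.8-11.5 | 0.31-0.34 | 0.021-0.026 | 0.40 / 0.014 |
| 48 accrued, 3.1 per month | 8.8-9.9 | 0.25-0.30 | 0.028-0.037 | 0.40 / 0.014 |
| 48 accrued, 4 per month | 7.2-8.6 | 0.21-0.27 | 0.034-0.050 | 0.40 / 0.014 |
| 1 year, 35 enrolled | 5.3-6.3 | 0.14-0.18 | 0.06-0.08 | 0.28 / 0.03 |
| 75 accrued, 3.1 per month | 16.9-18.0 | 0.50-0.54 | 0.006-0.008 | 0.62 / 0.003 |

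**5. Separate the causes at 48 and 3.1 per month.** P(success) falls from 0.69 to 0.40 before any lag. Nearly all of that is 48 instead of 75; the rest is the uncertain cases, the 90:42 split and the t in place of the normal. The lag then takes it to 0.25-0.30. P(futility) goes from 0.002 to 0.014, then to 0.028-0.037, so the lag multiplies it by about 2.0 to 2.6 (0.028/0.014 to 0.037/0.014).

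**6. Null values.** With no true difference, the p-value is uniform at any pair of counts, so 0.5 and 0.0088 stand. Simulation at 31 tumor and 7 injury labels gave 0.498 and 0.0084.

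**The case against.** Several points on the other side are sound.

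- **Attribution.** Setting the lagged 48-patient figures directly against 0.69 and 0.002 charges the lag with a gap that mostly comes from 48 versus 75. That is why each row above carries its fully labelled comparison.
- **Null behavior.** A reader might infer that all four stated probabilities fail, or that the false-positive rate is out of control. Neither is supported. The null pair holds. With 31/7 labels at the look and 90/42 at the end, the information fraction is about 0.20 rather than 0.5, yet overall type I error is only about 0.053 ignoring the futility rule and 0.046 applying it.
- **Share affected.** A reader might also infer that half of those counted cannot be injury cases. At 48 accrued, half is the upper end, and pathology can label injury early. Half is the expected share only under the 1-year trigger.
- **Practical loss.** A lower chance of early success only means that the study continues. In simulation at effect size 0.7, overall power with the lagged 48-patient look is about 0.94-0.95, against 0.97 with all 48 labelled. At 75 accrued the lag adds less than one percentage point to P(futility).
- **Unsettled clock.** Section 7.3 speaks of time from presentation of the lesion, while the follow-up paragraph of Section 1.0 counts from the study scans. At 4 per month the unlabelled share of 48 would be about 27% if the clock starts 12 weeks before enrolment and 73% if it starts 12 weeks after. Section 9.0 can also be read as requiring 6 months for every follow-up diagnosis. That would remove the tumor/injury asymmetry but make the look smaller still.
- **Existing flexibility.** Section 11.1 allows target accrual to rise if many outcomes are uncertain.

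These points limit the size of the problem but do not remove it. The accrual provision operates at the look itself. It neither postpones the test nor changes the futility rule.

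**Conclusion.** The point stands for the effect-size 0.7 probabilities only. The look is timed by accrual or the calendar, nothing delays it until labels mature, and the stated 0.69 and 0.002 describe a fully labelled look of about 75. At 48 accrued, over 2 to 4 per month, P(success) is about 0.21-0.34 and P(futility) about 0.021-0.050. The lag accounts for the part below 0.40 and above 0.014. The 1-year trigger is the worst case, with P(futility) of 0.06-0.08.

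Correcting 48 to 75 would not by itself restore the stated figures: at 75 accrued and 3.1 per month, the lag still takes P(success) from 0.62 to 0.50-0.54.

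The sizes rest on the outcome shares, early-label fractions, uniform accrual and enrolment-based clock set out above. The direction does not depend on the exact values. This is a planning fault worth correcting, not a threat to the trial's false-positive control.

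**What to change.** In Section 11.1:

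1. Trigger the interim when half of the planned patients (75 of 150, reconciled with the 48) have a final reference-standard label.
2. Count only patients enrolled long enough for either label to be reached, so that tumor and injury have equal opportunity. Keep pathology labels within that set; they should not be discarded for having come early.
3. Delete the 1-year trigger.
4. Restate the effect-size 0.7 stopping probabilities for the expected labelled counts. With 50 tumor and 25 injury labels they return to 0.67-0.69 and 0.002. If 48 labelled patients were kept at 2:1 (32/16), they would be about 0.44-0.46 and 0.011.
5. State whether the look has already been done, and on how many labelled lesions. Section 4.1 reports 75 patients accrued over 2 years, so both triggers had passed.
6. State one starting point for the 6-month clock, so that the counting rule can be applied.

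The cost is plan wording and a later look. For a given count, the delay is about 6 months, during which 12-24 more patients (6 × 2 to 6 × 4) enrol for scans that are standard of care. Moving from 48 to 75 adds a further 27/3.1, or about 9 months; that part belongs to reconciling the two counts.
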